7.4. MULTIPLE COMPARISONS/ MULTIPLICITY

No adjustment for multiplicity will be performed.

7.5. ACTIVE-CONTROL STUDY INTENDED TO SHOW EQUIVALENCE

For primary endpoint analysis, equivalence for efficacy will be supported if the two sided 95% confidence interval for the difference of mean change from baseline between two sequence groups for HbA1c is within $\pm 0.4\%$. Two-sided 95% CI will be derived using ANCOVA model which includes region, treatment sequence as fixed effects, and baseline HbA1c as a covariate.

7.6. EXAMINATION OF SUBGROUPS

No subgroup analysis is planned.

8. OUTPUT PRESENTATIONS

For safety and efficacy presentations, the order and naming of the treatment sequence group will be as follows.

- MYL-IG Seq (to Mylan's insulin glargine to Lantus® to Mylan's insulin glargine)
- Lantus® Seq (to Lantus® to Lantus® to Lantus® sequence group)

All descriptive safety and efficacy summaries will be presented by treatment sequence group and be broken down by visit for each period.

Document:	\\JEEDC-NAS01A\Biosdata\Mylan\INSULIN_GLARGINE\UXA25824\Biostatistics\Documentation\SAP		
Author:	[name] and [name]	Version Number:	Final V1.0
		Version Date:	[27JUL2016]

Template No: CS_TP_BS016 – Revision 3
Effective Date: 01May2012

Reference: CS_WI_BS005

9. DISPOSITION AND WITHDRAWALS

All patients who provide informed consent will be accounted for in this study.

The frequency and percentage of randomized patients who completed the trial or discontinued early will be summarized for each treatment sequence group. The comparison of patient discontinuations across treatment sequence groups will be performed using the Fisher's exact test. Reason for discontinuation from the study will also be summarized.

The number and proportion of patients withdrawing from the study during screening will be presented in a table. Additionally, the number and proportion of patients in each population will be summarized.

A listing of patients who did not meet the inclusion/exclusion criteria will be produced.

A list of significant protocol violations will be provided. A summary of significant protocol violations will also be provided as frequency and percentages, and treatment sequence group comparisons will be performed using the Fisher's exact test. Refer [Appendix 2](#) for significant protocol violation.

10. DEMOGRAPHIC AND OTHER BASELINE CHARACTERISTICS

Demographic data and other baseline characteristics will be presented for the randomized population.

Patient characteristics will be recorded prior to randomization or already collected in the MYL-GAI-3001 trial and will be listed and summarized by treatment sequence group. Overall summaries will include descriptive statistics for continuous measures (n, mean, standard deviation, median, minimum and maximum) and for categorical measures (n, frequency, and percent).

The following demographic and other baseline characteristics will be reported for this study:

- Age (years) - calculated relative to date of randomization
- Gender
- Race
- Weight (kg)
- Height (cm)
- Body Mass Index (BMI) (kg/m²)
- Duration of diabetes (years)
- Basal insulin timings (Morning/Evening)
- Baseline fasting plasma blood glucose
- Baseline HbA1c
- Fasting C-peptide, HIV, HBsAg, and HCVAb
- Region

Document:	\\JEEDC-NAS01A\Biosdata\Mylan\INSULIN_GLARGINE\UXA25824\Biostatistics\Documentation\SAP	Version Number:	Final V1.0
Author:	[name] and [name]	Version Date:	[27JUL2016]

Template No: CS_TP_BS016 – Revision 3
Effective Date: 01May2012

Reference: CS_WI_BS005

10.1. DERIVATIONS

- BMI (kg/ m²) = weight (kg)/ height (m)²
- Duration of diabetes (years) = (Date of screening – date of onset of diabetes+1) /365.25

10.2. STATISTICAL TESTS FOR BASELINE CHARACTERISTICS

Treatment sequence groups will be compared by using t-tests for quantitative measures and the Fisher's exact test or the chi-squared test for categorical measures to investigate if there are any significant differences in baseline characteristics. The p-value for the corresponding two-sided test will be presented.

11. MEDICAL HISTORY

Medical History information will be presented for the safety population, and coded using Medical Dictionary for Regulatory Activities (MedDRA) dictionary Version 18.1.

Medical history will be recorded at screening and will include pre-existing diseases or conditions reported at time of screening, which are resolved/stopped prior randomization, other than the study condition.

Frequency and percentage of Medical History conditions will be presented by treatment sequence groups and preferred term.

12. MEDICATIONS

Medications will be presented for the safety population and coded using WHO Drug dictionary 1DEC2015.

Prior and concomitant medications at enrollment will be summarized using ATC level 3 coding.

- 'Prior' medications are medications which started and stopped prior to the first dose of randomized study medication.
- 'Concomitant' medications are medications which:
 - o started prior to, on or after the first dose of randomized study medication,
 - o AND ended after the dose of randomized study medication or were ongoing at the end of the study.

See Appendix 1 for handling of partial dates for medications, in the case where it is not possible to define a medication as prior, concomitant, or post treatment, the medication will be classified by the worst case; i.e. concomitant.

Percentage of patients with at least 10% and overall concomitant medications will be summarized for each treatment period by treatment sequence groups as counts and percentages.

Document:	\\JEEDC-NAS01A\Biosdata\Mylan\INSULIN_GLARGINE\UXA25824\Biostatistics\Documentation\SAP	Version Number:	Final V1.0
Author:	[name] and [name]	Version Date:	[27JUL2016]

Template No: CS_TP_BS016 – Revision 3
Effective Date: 01May2012

Reference: CS_WI_BS005

12.1. STATISTICAL TEST FOR CONCOMITANT MEDICATION

Treatment sequence groups for percentages of patients with at least 10% and overall concomitant medications will be compared using Chi-square test. P-value for the corresponding two-sided test will be presented.

13. STUDY MEDICATION EXPOSURE

Total treatment duration (in days) will be summarized for each treatment sequence and by period. The sequence group will be compared using t-test. Descriptive statistics for continuous measures will be presented along with the p-value for treatment sequence comparison.

Interruptions, compliance, and dose changes are not taken into account for duration of exposure.

13.1. DERIVATIONS

Total treatment duration = date of last intake of study medication prior to the scheduled visit (Week 36) – date of first intake of study medication + 1.

It will be presented in days.

14. STUDY TREATMENT NON-COMPLIANCE

Patient will be identified as study treatment non-compliant if the patient meets any following criteria:

- Missing either total meal time insulin or basal insulin doses for 5 consecutive days.
- Missing either total meal time insulin or basal insulin doses for more than 30 accumulative days for completer or more than 20% treatment days for drop-out.
- Taking more than one administration of basal insulin (If multiple injections are required to deliver the required quantity of drug due to logistic reasons, then it is considered as one administration) for 10 days cumulative.
- Taking more than the prescribed basal insulin dose for more than 30 days cumulative.

Number and proportion of patients with noncompliance will summarized along with individual reasons for non-compliance.

15. EFFICACY OUTCOMES

Summaries will include descriptive statistics for continuous measures (n, mean, standard deviation, median, minimum and maximum) and for categorical measures (n, frequency, and percent).

Document:	\\JEEDC-NAS01A\Biosdata\Mylan\INSULIN_GLARGINE\UXA25824\Biostatistics\Documentation\SAP	Version Number:	Final V1.0
Author:	[name] and [name]	Version Date:	[27JUL2016]

Template No: CS_TP_BS016 – Revision 3
Effective Date: 01May2012

Reference: CS_WI_BS005

15.1. PRIMARY EFFICACY

15.1.1. PRIMARY EFFICACY VARIABLE & DERIVATION

The primary efficacy outcome is change in HbA1c from baseline at week 36. .

15.1.2. MISSING DATA METHODS FOR PRIMARY EFFICACY VARIABLE

The imputation will not be applied. If week 36 HbA1c is missing then last non-missing values from period 3 will be used.

15.1.3. PRIMARY ANALYSIS OF PRIMARY EFFICACY VARIABLE

The primary objective of this study is to test the equivalence of changes in HbA1C between two treatment sequence groups at week 36.

The primary efficacy analysis will be performed for the mITT population.

ANCOVA will be performed on the primary outcome variable and the model will include region and sequence group as fixed effect and baseline value (52 weeks in MYL-GAI-3001) as covariate using mITT population. A 95% confidence interval for the difference between two treatment sequence groups for mean change from baseline HbA1c at endpoint will be produced using the ANCOVA method. Equivalence of Mylan's insulin glargine sequence group to Lantus® sequence group will be established if the 95% confidence interval is within $\pm 0.4\%$ equivalence limits.

The Least Square (LS) means for each treatment sequence group and associated standard errors will be derived. Differences in LS means will be calculated and associated 2-sided 95% confidence intervals will be provided.

15.1.4. SENSITIVITY ANALYSIS OF PRIMARY EFFICACY VARIABLE(S)

A further robustness check will be conducted using the PP population and applying the same ANCOVA procedure as described in [Section 15.1.3](#). Any differences in the conclusion will be further investigated by examining differences between the mITT and the PP populations.

Additional sensitivity analysis will be performed based on MMRM ANCOVA from secondary efficacy analysis. A repeated measures analysis employing a restricted maximum likelihood (REML)-based, mixed-effects model approach (MMRM) will be used to produce a 95% confidence interval for the difference between Mylan's insulin glargine sequence and Lantus® sequence for mean change of HbA1c at week 36. The MMRM model will include the fixed, categorical effect of treatment sequence group, region, visit, treatment sequence-by-visit interaction and baseline value (52 weeks in MYL-GAI-3001) as covariates.

A further robustness check will be done using the PP population and applying the same MMRM procedure as described in [Section 15.1.3](#) to establish equivalence. Any differences in conclusions will be further investigated by examining differences in the ITT and the PP populations.

Other sensitivity analysis addressing missing data be conducted as following

Document:	\\JEEDC-NAS01A\Biosdata\Mylan\INSULIN_GLARGINE\UXA25824\Biostatistics\Documentation\SAP		
Author:	[name] and [name]	Version Number:	Final V1.0
		Version Date:	[27JUL2016]

Template No: CS_TP_BS016 – Revision 3
Effective Date: 01May2012

Reference: CS_WI_BS005

Copyright © 2012 Quintiles Transnational Corp. All rights reserved.

The contents of this document are confidential and proprietary to Quintiles Transnational Corp. Unauthorized use, disclosure or reproduction is strictly prohibited.

Multiple imputed datasets will be generated based on the assumption of a monotone missing data pattern. The imputation will be performed using the monotone regression method for week 24 and week 36 sequentially. The variables treatment region, previous exposure to insulin and basal insulin dosing time will be used as independent variables.

An example of the SAS code using monotone regression for multiple imputation for week 36 (visit 13).

```
PROC MI DATA=XXX OUT=OXXX NIMPUTE=100 SEED=1122015;  
  VAR Baseline VISIT13 VISIT9 VISIT5 ARMCD PSTRTRGN;  
  CLASS ARMCD PSTRTRGN;  
  MONOTONE REG (VISIT5 = BASELINE ARMCD PSTRTRGN);  
  MONOTONE REG (VISIT9 = BASELINE VISIT5 ARMCD PSTRTRGN);  
  MONOTONE REG (VISIT13 = BASELINE VISIT9 VISIT5 ARMCD PSTRTRGN);
```

RUN;

Imputation for the week 36 will be performed using the set with values imputed. In case non-monotone missing data (usually relatively infrequent) will be imputed using the Markov Chain Monte Carlo (MCMC) option prior to the above regression approach.

All imputed datasets will be analyzed using the same model parameters as used in the additional sensitivity analysis, and the results will be combined using Rubin's rules

An example of the SAS code for combining results using Rubin's rules with PROC MIANALYZE is given below:

ODS OUTPUT PARAMETERESTIMATES=MIESTDIFF ;

```
PROC MIANALYZE DATA=LSDIFF;  
  MODELEFFECTS LSMEANSDIFF;  
  STDERR STDERR;
```

RUN;

This approach will be performed for the ITT and the PP populations.

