7.3. MISSING DATA

Missing primary and secondary efficacy and safety analysis data will be not imputed except when week 36 HbA1c data is missing due to early discontinuation, exit measurement of that period will be used for endpoint. In addition, for sensitivity analysis of multiple imputation method, if missing values occur in more than 10% of the patients for HbA1C values, then monotone regression for multiple imputations will be used.

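### The multiple-imputation sensitivity analysis in SAP 15.1.4 cannot be run as described: the variable order makes ordinary dropout non-monotone, and text and code name different predictors and visits

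*SAP*

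**What the plan says.** SAP 15.1.4 introduces the imputation as a sensitivity analysis for missing data, to be done in the ITT and PP populations. Its elements are:

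- **Pattern:** "Multiple imputed datasets will be generated based on the assumption of a monotone missing data pattern".
- **Visits, text:** "The imputation will be performed using the monotone regression method for week 24 and week 36 sequentially".
- **Predictors, text:** "The variables treatment region, previous exposure to insulin and basal insulin dosing time will be used as independent variables".
- **Variable order, example code:** "VAR Baseline VISIT13 VISIT9 VISIT5 ARMCD PSTRTRGN". VISIT5, VISIT9 and VISIT13 are weeks 12, 24 and 36.
- **Regressions, example code:** three lines, from "MONOTONE REG (VISIT5 = BASELINE ARMCD PSTRTRGN" for week 12 to "MONOTONE REG (VISIT13 = BASELINE VISIT9 VISIT5 ARMCD PSTRTRGN" for week 36.
- **Fallback:** "In case non-monotone missing data (usually relatively infrequent) will be imputed using the Markov Chain Monte Carlo (MCMC) option", before the regression step.

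SAP 7.3 says that monotone regression will be used "if missing values occur in more than 10% of the patients for HbA1C values". SAP 15.1.4 and SAP 3.3 state the analysis with no such condition.

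**The concern.** The primary analysis uses the mITT population (SAP 5.4), which leaves out anyone without a period 3 HbA1c. Only the ITT repeated-measures model and this imputation bring those patients back, and this is the one presented as the answer to missing data. It should therefore be possible to program it in one way only.

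As drafted, two competent programmers could produce different analyses. One would follow the text, the other the code, and the code's variable list runs against its own regression lines. Direction matters as well: an imputation model without arm pulls the groups together, which in an equivalence trial is the lenient direction.

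**Working it through.** **Inputs.** 69 per arm, SD 0.61, margin ±0.4, 10% without usable HbA1c, planned power 90% (Protocol 9.1, SAP 3.1); two-sided 95% interval (SAP 6.5). Variable lists and regressions are from SAP 15.1.4.

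**The plan's own figure.** 69 × 0.9 ≈ 62 per arm. SE = 0.61 × √(2/62) = 0.1096. Power = 2Φ(0.4/0.1096 − 1.96) − 1 = 2Φ(1.69) − 1 = 90.9% (90.4% with the t distribution). The stated 90% reproduces, so these inputs are used below.

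**Step 1: is dropout monotone in the listed order?** A pattern is monotone if, once a variable is missing, every variable listed after it is missing too.

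| Pattern | Missing | Full list as written | Four HbA1c variables only, as written | Arm, region, baseline, weeks 12, 24, 36 |
|---|---|---|---|---|
| Leaves before week 12 | weeks 12, 24, 36 | no | yes | yes |
| Leaves after week 12 | weeks 24, 36 | no | no | yes |
| Leaves after week 24 | week 36 | no | no | yes |

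Four intermittent patterns were also checked (week 12 only; week 24 only; weeks 12 and 24; weeks 12 and 36). None is monotone in the full list as written, so 0 of 7 incomplete patterns qualify. In time order only these intermittent gaps remain non-monotone, and they are what an MCMC step is for.

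**Step 2: covariates listed after their target.** In the order as written: week 12 regression, 2 (arm, region); week 24, 3 (week 12, arm, region); week 36, 4 (weeks 24 and 12, arm, region). In time order: none.

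**Step 3: text against code.**

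| | Text | Code |
|---|---|---|
| Baseline HbA1c | not named | used |
| Earlier HbA1c | not named | used |
| Arm | only if a comma is missing between treatment and region | used |
| Region | named | used |
| Previous insulin exposure | named | absent |
| Basal dosing time | named | absent |
| Visits imputed | weeks 24, 36 | weeks 12, 24, 36 |

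**Step 4: size of the effect if the text is followed literally.** With neither arm nor earlier HbA1c in the model, imputed values have about the same mean in both arms. With a fraction p missing in each arm, the expected difference is (1 − p) × 0.40: 0.9 × 0.40 = 0.36 and 0.85 × 0.40 = 0.34.

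Simulation, with true difference 0.40 (at the margin), 69 per arm, SD 0.61, missing at random, 6,000 trials, 20 imputations (the SAP code asks for 100) and Rubin's rules. The between-visit correlation of 0.7 is an assumption; the documents give none. Monte Carlo error is about √(0.025 × 0.975/6000) = 0.2 percentage points.

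| Imputation model | 10% missing: estimate, false equivalence | 15% missing: estimate, false equivalence |
|---|---|---|
| Arm and earlier HbA1c (code's key predictors) | 0.40, 2.5% | 0.40, 2.4% |
| Earlier HbA1c, no arm | 0.39, 2.7% | 0.38, 2.5% |
| Neither (text, literally) | 0.36, 4.0% | 0.34, 4.9% |

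Further runs of the last row gave 3.6% to 4.1% and 4.2% to 5.5%, hence about 4% and about 5%. The middle row matches a difference already present at the earlier visit: pooled slope (0.7 × 0.61² + 0.4²/4)/(0.61² + 0.4²/4) = 0.3005/0.4121 = 0.73, so the estimate is 0.36 + 0.10 × 0.73 × 0.40 = 0.39. With no difference at the earlier visit, that row would shrink much like the last.

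**Step 5: the condition in SAP 7.3.** More than 10% of 138 means 14 or more patients. The binomial probability of that is 0.01, 0.22, 0.52, 0.79 and 0.96 for true missing rates of 5%, 8%, 10%, 12% and 15%.

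**The case against.** Several counter-arguments have force.

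- **The code is labelled an example**, and its regression lines run in correct time order with arm, region and baseline in all three. Followed for its predictors, it gives no material bias. This stands, and it limits the harm in Step 4 to one reading of the text.
- **The text can be read kindly.** A lost comma between treatment and region would restore arm, and sequential imputation suggests conditioning on earlier visits. This is plausible, but even so the text does not name baseline or earlier HbA1c, and the code omits two predictors that the text does name.
- **Non-monotone data have a stated route.** True, and nothing here shows that the MCMC route is biased. The variable order has no measured effect on the estimate; the defect is that the method described would not be the method doing the work.
- **Other cover exists.** The ITT repeated-measures model also keeps patients with earlier post-baseline HbA1c, and SAP 15.2 maps an off-schedule last value to the next scheduled visit. This lowers the stakes.

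Three stronger inferences are tempting but not supported:

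1. That previous insulin exposure is constant because everyone has had 52 weeks of Lantus. The Protocol's Schedule of Activities carries insulin usage history over from MYL-GAI-3001, and exposure before that study may differ.
2. That SAP 7.3 and 15.1.4 flatly contradict each other. One can be read as saying when and the other how. They need reconciling, but error is not proven.
3. That the 10% condition is a coin toss. The 0.52 holds only if its count is the same as the planned 10% lacking baseline or last-period HbA1c. SAP 7.3 names neither visit nor population.

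**Conclusion.** The concern holds for the multiple-imputation sensitivity analysis as specified. The listed order makes all three ordinary dropout patterns non-monotone, and the text and code disagree on predictors and visits. That dropout would fall to the MCMC step assumes that the program takes the order from the variable list; this is its usual behaviour, but the documents do not say so.

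The numerical harm is conditional. Only the literal text, without arm and earlier HbA1c, takes a true 0.40 to about 0.36 (10% missing) or 0.34 (15%), with false equivalence going from about 2.5% to about 4% or 5%. These rates describe this sensitivity analysis. A reader might take them as the trial's error rate, but SAP 7.5 and 15.1.3 rest equivalence on the mITT ANCOVA alone. That analysis, its interval and the sample size are untouched.

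**What to change.** - Order the variable list as ARMCD PSTRTRGN BASELINE VISIT5 VISIT9 VISIT13, and keep the regression lines in time order.
- Give one predictor list in text and code: arm, region, baseline HbA1c and all earlier HbA1c. Dosing time and prior insulin exposure are optional, if they vary among these patients.
- Name one set of imputed visits in text and code.
- Reconcile SAP 7.3 with 15.1.4 and 3.3, preferably by always reporting the ITT imputation. If the 10% condition stays, say which visit and which population it counts.

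The cost is SAP wording and a few lines of code before database lock. There is no change to data collection, sample size or the primary analysis.

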15.2. SECONDARY EFFICACY

The secondary efficacy analyses will be performed for the ITT population.

A repeated measures analysis employing a restricted maximum likelihood (REML)-based, mixed-effects model approach (MMRM) will be used to compare treatment sequence difference at scheduled visits. The MMRM model will include the fixed, categorical effect of treatment sequence group, region, visit, treatment sequence-by-visit interaction and baseline value (52 weeks in MYL-GAI-3001) as covariates. The data collected at Baseline, all schedule visits will be used in the MMRM model for the purpose of analysis. For the drop-out patients, if the last post baseline data is not falling at the scheduled visit, then it will be mapped to the next scheduled visit and this data will also be included in the analysis.

An unstructured covariance matrix will be used to model the within-patient errors. The Kenward-Roger approximation will be used to estimate denominator degrees of freedom. If the model for unstructured covariance matrix fails to converge, the heterogeneous Toeplitz covariance structure, followed by heterogeneous autoregressive covariance structure, will be used. If a structured covariance matrix is used because of the convergence

Document:	\\JEEDC-NAS01A\Biosdata\Mylan\INSULIN_GLARGINE\UXA25824\Biostatistics\Documentation\SAP		
Author:	[name] and [name]	Version Number:	Final V1.0
		Version Date:	[27JUL2016]

Template No: CS_TP_BS016 – Revision 3
Effective Date: 01May2012

Reference: CS_WI_BS005

Copyright © 2012 Quintiles Transnational Corp. All rights reserved.

The contents of this document are confidential and proprietary to Quintiles Transnational Corp. Unauthorized use, disclosure or reproduction is strictly prohibited.

problem, an analysis will be conducted where a sandwich estimator will be used for the fixed effects parameters to take account of possible misspecification of the true covariance matrix.

Above mentioned statistical analysis approach will be performed for all secondary continuous efficacy variables. Contrasts of LS mean at each scheduled visit will be used to evaluate all pairwise treatment sequence group comparisons, and 95% confidence intervals for treatment sequence group differences in LS means will be computed for each visit.

Following efficacy measures (both actual and change values) will be summarized at baseline (week 52 in MYL-GAI-3001) and scheduled visits.

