## **9. DATA ANALYSIS/STATISTICAL METHODS**

### **9.1 Sample Size Determination**

Approximately 138 patients with type 1 diabetes will participate in this trial. Approximately 69 patients will be randomized to one of the two sequence groups (Mylan sequence group: Mylan's insulin glargine switch to Lantus® sequence group and switch back to Mylan's insulin glargine or Lantus Sequence Group: Lantus® to Lantus® to Lantus® sequence group) in a 1:1 ratio. No replacement of patient will be performed if patient discontinued prematurely from the study. For the modified intent-to-treat (mITT) population, power to demonstrate equivalence with  $\pm 0.4\%$  limits will be 90% with 10% patients who don't have at least one baseline and one last period HbA1c data. The power is calculated assuming no true mean group difference and a 0.61% standard deviation. This standard deviation is based on published results for clinical studies with Lantus® [12].

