3.1. GENERAL DESCRIPTION

Study Duration:

The maximum possible duration of patient participation in the extension trial is 40 weeks, which includes:

- Treatment period 1: 12 weeks (Week 0 to Week 12).
- Treatment period 2: 12 weeks (Week 12 to Week 24).
- Treatment period 3: 12 weeks (Week 24 to Week 36).
- Follow-up period: 4 weeks follow-up visit (Week 36 to Week 40)

Number of Patients:

Approximately 138 patients with type 1 diabetes who completed the 3001 study on the Lantus will participate in this trial. Approximately 69 patients will be randomized to one of two sequence groups (Treatment sequence arm 1: Mylan's insulin glargine switch to Lantus® sequence group and switch back to Mylan's insulin glargine, or Treatment sequence arm 2: Lantus® to Lantus® to Lantus® sequence group) in a 1:1 ratio. No replacement of patients will be performed if a patient discontinued prematurely from the study. For the modified intent-to-treat (mITT) population, power to demonstrate equivalence with $\pm 0.4\%$ limits will be 90% with 10% patients who don't have at least one baseline and one last period HbA1c data. The power is calculated assuming no true mean group difference and a 0.61% standard deviation. This standard deviation is based on published results for clinical studies with Lantus®.

Allocation to Treatment

Patients who completed the 3001 study on Lantus® will be randomized 1:1 to receive either Mylan's insulin glargine or Lantus® using an IVRS/IWRS. Change of dosing from morning to bedtime or vice versa will not be permitted. If a patient discontinues, the patient will not be allowed to re-enter the extension study.

Blinding

This is an open-label study. To minimize bias, treatment assignments will not be revealed to the central laboratory for the safety (immunogenicity) and efficacy (HbA1c) analyses.

Document:	\\IEEDC-NAS01A\Biosdata\Mylan\INSULIN_GLARGINE\UXA25824\Biostatistics\Documentation\SAP		
Author:	[name] and [name]	Version Number:	Final V1.0
		Version Date:	[27JUL2016]

[figure not shown]
Template No: CS_TP_BS016 – Revision 3
Effective Date: 01May2012

Reference: CS_WI_BS005

Study Treatment

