17.6.2. IMMUNOGENICITY PROFILES ANALYSES

Following parameters will be summarized for immunogenicity.

- Total Insulin Antibodies
 - Percent Binding (%B/T, Continuous outcome)
 - Positive/Negative (Categorical outcome)
- Cross Reactive Insulin Antibodies
 - Percent Binding (%B/T, Continuous outcome)
 - Positive/Negative (Categorical outcome)

Document:	\\JEEDC-NAS01A\Biosdata\Mylan\INSULIN_GLARGINE\UXA25824\Biostatistics\Documentation\SAP	Version Number:	Final V1.0
Author:	[name] and [name]	Version Date:	[27JUL2016]

Template No: CS_TP_BS016 – Revision 3
 Effective Date: 01May2012

Reference: CS_WI_BS005

Copyright © 2012 Quintiles Transnational Corp. All rights reserved.

The contents of this document are confidential and proprietary to Quintiles Transnational Corp. Unauthorized use, disclosure or reproduction is strictly prohibited.

- Insulin(Drug) Specific Antibody
 - Percent Binding (%B/T, Continuous outcome)
- Anti-HCP
 - Positive/Negative (Categorical outcome)

Immunogenicity profiles with continuous variables (% binding) will be analyzed using the MMRM method for each assay, similar to change from baseline efficacy analyses. The model will include the terms region, treatment sequence group, visit, treatment sequence group-by-visit as fixed effects, and baseline value as covariate. The treatment sequence group difference and 95% confidence intervals will be constructed using the model at scheduled visits. In case the normal distribution assumption is severely violated, then non-parametric analysis will be performed using Wilcoxon rank-sum test for treatment sequence group comparison, Hodges Lehmann's estimator will be used to compute the median difference between the treatment sequence groups and the corresponding 95% confidence interval. Safety population will be used for ADA continuous variables. Immunogenicity profiles with dichotomous outcomes will be summarized with frequency and percentage at scheduled visits for each assay. Treatment sequence group comparison will be performed using Fisher's exact test. P-value for the two-sided test will be presented.

Correlation analyses of insulin cross-reactive antibodies with clinical factors such as HbA1c and insulin doses will be performed by treatment sequence group along with graphics to explore relationship of insulin antibodies with such factors for each assay method used. Additionally, mean (\pm SD) and median (IQR) for actual measurements by visit will also be presented.

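### Every MMRM in the SAP uses one baseline slope for all visits, which can cost week-36 precision and keeps the HbA1c robustness MMRM from reproducing the primary ANCOVA

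*SAP*

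**What the plan says.** SAP 15.2 sets the general MMRM for secondary efficacy: "categorical effect of treatment sequence group, region, visit, treatment sequence-by-visit interaction and baseline value (52 weeks in MYL-GAI-3001) as covariates", with an unstructured covariance matrix first. SAP 15.1.4 repeats this model for HbA1c, where it "will be used to produce a 95% confidence interval for the difference between" the two sequences at week 36. SAP 3.3 gives that analysis the role of a robustness check on the primary result.

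The same terms recur for HbA1c, fasting plasma glucose, SMBG and insulin dose (SAP 15.2.3), laboratory values (17.2), vital signs (17.4), immunogenicity (17.6.2) and hypoglycemia rate (17.6.3). For immunogenicity: "The model will include the terms region, treatment sequence group, visit, treatment sequence group-by-visit as fixed effects, and baseline value as covariate". Protocol 9.8, 9.9.2, 9.9.3 and 9.9.5 have the same structure. No section has a baseline-by-visit or region-by-visit term.

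The primary analysis (SAP 15.1.3) is a separate ANCOVA at week 36 with sequence group, region and baseline. The multiple-imputation code in SAP 15.1.4 regresses each HbA1c visit on baseline and region separately, but the completed datasets are then analyzed with the single-slope MMRM.

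**The concern.** The dependent variable is change from baseline. If the correlation with baseline fades over 36 weeks, the slope of change on baseline becomes more negative from visit to visit. A single coefficient is then a weighted average over visits. In the scenarios examined the weight lies mainly on the early visits, so week 36 is adjusted with the wrong slope. SAP 2.2 names 36 weeks as the time of comparison for the secondary objectives, so any loss falls on the contrast of interest.

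The second issue is interpretation. When the HbA1c MMRM and the ANCOVA differ, a reader will want to attribute the gap to missing data. As written, the gap also contains a difference in covariate adjustment. The follow-up described in SAP 15.1.4 compares analysis populations (mITT or ITT against PP), which would not reveal that cause.

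The imputation and analysis models also disagree: the first allows visit-specific baseline and region effects, the second does not.

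**Working it through.** **Reproducing the plan's own figure.** Inputs from Protocol 9.1, SAP 3.1 and SAP 15.1.3:
- "Approximately 138 patients with type 1 diabetes will participate in this trial", randomized 1:1
- "limits will be 90% with 10% patients who" lack the required HbA1c values, so 138 × 0.9 / 2 ≈ 62 per arm
- "The power is calculated assuming no true mean group difference and a 0.61% standard deviation"
- decision rule: "95% confidence interval is within $\pm 0.4\%$ equivalence limits"

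Standard error = 0.61 × √(2/62) = 0.1096. Power = 2Φ(0.4/0.1096 − 1.96) − 1 = 2Φ(1.691) − 1 = 0.909, or 0.904 with the exact t distribution. The stated 90% reproduces. It belongs to the ANCOVA, so the MMRM terms do not affect it.

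**Formula for the loss.** With complete data, randomization and an unstructured matrix Σ of residual covariances between visits:
- common slope β_c = (1′Σ⁻¹β)/(1′Σ⁻¹1), where β holds the visit-specific slopes
- week-36 variance ratio, common slope to visit-specific slope = 1 + (β₃₆ − β_c)² × var(baseline) / residual variance at week 36

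The ratio is 1 when all slopes are equal. This is a large-sample formula.

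**HbA1c by hand.** Assumptions, none from the documents: equal variances scaled to 1, and baseline correlations 0.85, 0.75 and 0.65 at weeks 12, 24 and 36.
- Slopes on change (correlation − 1): −0.15, −0.25, −0.35.
- Residual variances (1 − correlation²): 0.2775, 0.4375, 0.5775.
- With no residual correlation between visits, the weights are proportional to 1/variance: 0.473, 0.300, 0.227.
- β_c = −(0.473 × 0.15 + 0.300 × 0.25 + 0.227 × 0.35) = −0.225.
- Ratio = 1 + (−0.350 + 0.225)² / 0.5775 = 1.027.

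With autoregressive residual correlation 0.9 per 12 weeks instead, β_c = −0.101 and the ratio is 1 + 0.249² / 0.5775 = 1.107. The between-visit correlation therefore matters as much as the baseline correlation.

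**Range of the formula.** Baseline correlation falls linearly; residual correlation is exchangeable 0-0.7 or autoregressive 0.5-0.9 per 12 weeks.

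| Outcome | Baseline correlation | Variance ratio |
|---|---|---|
| HbA1c, 3 visits | 0.85 to 0.77 | 1.01 |
| HbA1c, 3 visits | 0.85 to 0.65 | 1.03-1.11 |
| 12 visits | 0.95 to 0.80 | 1.02-1.13 |
| 12 visits | 0.90 to 0.60 | 1.05-1.28 |
| 12 visits | 0.70 to 0.50 | 1.02-1.06 |

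In interval width, √1.11 = 1.05 and √1.28 = 1.13, so at most about 5% and 13% wider.

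**Simulation of the HbA1c check.** Complete data, 62 per arm, 2,000 runs per scenario. Assumed: baseline SD 0.7-1.0, residual SDs 0.45/0.55/0.61, autoregressive correlation 0.7, one third of patients in one region. Drift is the change in slope from week 12 to week 36; gap is the mean absolute difference between the two week-36 estimates, in HbA1c points.

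| Drift | Variance, SAP MMRM / ANCOVA | Gap | Runs with a different equivalence verdict | Power, ANCOVA vs SAP MMRM |
|---|---|---|---|---|
| 0 | 0.99-1.00 | 0.007 | about 1% | 0.90-0.91 vs 0.90-0.92 |
| 0.2 | 1.02-1.04 | 0.017-0.022 | 4-5% | 0.89-0.90 vs 0.89-0.90 |
| 0.3 | 1.06-1.13 | 0.024-0.034 | 6-8% | 0.89 vs 0.84-0.87 |
| 0.4 | 1.16-1.26 | 0.032-0.044 | 8-15% | 0.89-0.90 vs 0.78-0.85 |

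The correlations 0.85 to 0.65 above correspond to drift 0.2; drifts of 0.3 and 0.4 are steeper than any HbA1c case in the first table. Adding baseline-by-visit alone brings precision back to that of the ANCOVA (standard error 0.110 in both), but leaves a gap of 0.004-0.005, or 0.010 if the region effect drifts by 0.2. Exact agreement requires region-by-visit as well.

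**The case against.** A prespecified common slope is a valid model under randomization, and the documents contain nothing from which to estimate drift. Patients enter after 52 weeks on Lantus and titration is to be kept to a minimum, so slopes may be nearly constant. The common-slope model would then be equal or marginally better. This stands: the loss is conditional, and its size is not known.

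The idea that early, highly correlated visits dominate the slope fits outcomes measured from week 2, such as SMBG, antibodies and vital signs. It does not fit HbA1c or laboratory values (weeks 12, 24 and 36 only) in that form, and fasting plasma glucose starts at week 8. That also stands, and it is why HbA1c has a separate, smaller range.

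The SAP does not promise that the MMRM will equal the ANCOVA. It names multiple imputation as the analysis that addresses missing data. The MMRM also uses ITT rather than mITT, and drop-out values that fall off schedule are mapped to the next visit. The proposed terms would therefore remove one source of disagreement, not all. But the imputation analysis reuses the single-slope MMRM, so it does not avoid the problem.

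For antibody levels and hypoglycemia rate, a rank test replaces the MMRM if normality is severely violated; the change then has no effect on those comparisons.

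**Conclusion.** The point holds as an inexpensive improvement. All the MMRMs use one baseline slope. If the true slope shifts over visits, week-36 precision falls. Under the assumed correlations the variance is roughly 1-11% larger for HbA1c and roughly 2-28% larger for twelve-visit outcomes; it is no larger if slopes are constant. Neither the baseline correlations nor the between-visit correlations come from the documents.

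The HbA1c MMRM cannot reproduce the week-36 ANCOVA even with complete data, because neither baseline nor region is crossed with visit.

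A reader might infer three stronger things that the documents do not support:
- That the plan does lose precision. This depends on an unreported drift.
- That the baseline term alone explains the mismatch with the ANCOVA. Region contributes too.
- That the primary conclusion is at risk. The ANCOVA, its error rate and its power do not depend on these terms, and no bias arises under randomization.

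**What to change.** Before database lock, add baseline-by-visit to every MMRM in SAP 15.1.4, 15.2, 17.2, 17.4 and 17.6. In the HbA1c MMRM add region-by-visit too, and use the same model for the completed datasets after multiple imputation, so that the analysis model matches the imputation models. State in SAP 15.1.4 that any remaining difference between MMRM and ANCOVA can still reflect ITT versus mITT and the forward mapping of drop-out values.

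The cost is a small change to wording and code. With two regions and three visits, HbA1c gains four parameters (two for baseline, two for region). Twelve-visit outcomes gain up to eleven, against about 124 evaluable patients. If the slopes are in fact equal, efficiency is marginally lower.
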